3. DESCRIPTION OF DESIGN AND TRIAL POPULATION

3.1 OVERALL TRIAL DESIGN AND PLAN

This confirmatory multi-national, randomized, double-blind, double dummy, active controlled, parallel design study compares BI 655066 with adalimumab. In total, approximately 600 patients with moderate to severe chronic plaque psoriasis will be randomized in this trial.

Patients are included in the study once they have signed the informed consent. Patients suitable after screening will be eligible to participate in the 44 week treatment period and will be randomized at a ratio of 1:1 to one of 2 treatment arms (BI 655066 or adalimumab) shown in [Figure 3.1: 1](#).

Patients initially randomized to BI 655066 will stay on BI 655066.

At Week 16, patients initially on adalimumab and <PASI 50 will be switched to BI 655066.

At Week 16, patients initially on adalimumab and \geq PASI 90 will stay on adalimumab.

At Week 16, patients initially on adalimumab and \geq PASI 50 and <PASI 90 will be re-randomised 1:1 to receive either BI 655066 or adalimumab.

[figure not shown]

Figure 3.1: 1 Trial design

Patients will be blinded to treatment. Patients in each dose group will receive the same injections (active or placebo) at each designated time point, in order to maintain blinding.

Patients starting and continuing with BI 655066 active drug will receive 2 syringes of BI 655066 active drug (2 x 75mg) at randomization, at Weeks 4, 16 and 28 and placebo adalimumab at randomization (2 syringes) and 1 placebo adalimumab syringe at Weeks 1, 3, 5, 7, 9, etc. up to Week 41. These patients also receive 2 syringes of BI 655066 placebo at Weeks 20 and 32 to maintain blinding to the BI 655066 active treatment arm starting at Week 16 after adalimumab pre-treatment. BI 655066 active treatment always starts with a loading dose 4 weeks after the first injection.

Patients starting with active adalimumab and switching to active BI 655066 at Week 16 will receive 2 syringes active adalimumab at randomization (2 x 40mg) followed by 1 syringe active adalimumab (40mg) at Weeks 1, 3, 5, 7, 9, 11, 13, 15; and 1 placebo adalimumab syringe at Weeks 17, 19, 21, etc. up to Week 41 to maintain blinding. These patients also receive 2 syringes of BI 655066 placebo at randomization and Week 4 followed by two active BI 655066 injections (2 x 75mg) at Weeks 16, 20 and 32 as well as 2 placebo BI 655066 injections at Week 28.

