5.3.7 Adverse event collection and reporting

AE Collection

The following must be collected and documented on the eCRF by the Investigator (see [Figure 5.3.7: 1](#))

- From signing the informed consent onwards through the Residual Effect Period (REP), until individual patient's end of trial; all AEs (serious and non-serious) and all AESIs must be collected
- After the individual patient's end of trial: the investigator does not need to actively monitor the patient for AEs but should only report relevant SAEs and relevant AESIs of which the investigator may become aware of.

[figure not shown]

Figure: 5.3.7: 1 Adverse Events Collection

The REP is defined as 15 weeks after the last administration of BI 655066 (active or placebo). All AEs which occurred through the treatment phase and throughout the REP will be considered as on treatment; please see [Section 7.3.4](#). Events which occurred after the REP will be considered as post treatment events.

AE reporting to sponsor and timelines

The Investigator must report SAEs, AESIs, and non-serious AEs which are relevant for the reported SAE or AESI, on the BI SAE form via fax immediately (within 24 hours) to the Sponsor's unique entry point (country specific contact details will be provided in the ISF).

The same timeline applies if follow-up information becomes available. In specific occasions the Investigator could inform the Sponsor upfront via telephone. This does not replace the requirement to complete and fax the BI SAE form.

With receipt of any further information to these events, a follow-up SAE form has to be provided. For follow-up information the same rules and timeline apply as for initial information.

Information required

For each AE, the Investigator should provide the information requested on the appropriate eCRF pages and the BI SAE form, e.g. onset, end date, intensity, treatment required, outcome, seriousness, and action taken with the investigational drug(s). The Investigator should determine the causal relationship to the trial medication.

The following should also be recorded as an (S)AE in the eCRF and SAE form (if applicable):

- Worsening of the underlying disease or of other pre-existing conditions
- Changes in vital signs, ECG, physical examination and laboratory test results, if they are judged clinically relevant by the Investigator.

If such abnormalities already pre-exist prior trial inclusion they will be considered as baseline conditions.

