6.2.3.1 Early treatment and trial termination

If study medication is discontinued prior to the planned [Flow Chart](#) visit EOT, every effort should be made to have the patient continue in the trial and complete all of the remaining trial visits and procedures including EOT and EOO Visit; with the EOO Visit to be performed 4 weeks after the EOT Visit.

If a patient cannot or will not continue in the trial, the patient should complete EOT Visit procedures instead of the next planned treatment period visit. These patients should be registered as prematurely discontinued in IRT and return to the clinic for End of Observation Visit 16 (± 1) weeks after their last administered dose of BI 655066 (active or placebo). Patients who discontinue from the trial prematurely will not have the option to participate in the open label extension (OLE) study.

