6.2.3.2 Trial completion

Patients who complete the randomized treatment period and who qualify for the open-label extension (OLE) study will continue treatment with active BI 655066 and therefore will not have a Follow-up Visit in study 1311.30.

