6.2.3.3 Vital Status

Randomised patients who do not participate in the OLE study and who withdraw from the study prior to their planned EOO Visit will be contacted for their vital status assessment

(alive / dead / lost to follow-up). In case the patient died, an SAE form should be completed by the site and forwarded immediately to the sponsor. Vital status assessment should occur at 48 (\pm 1) weeks after randomisation.

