9.0 Study Drug Exposure and Compliance

Summary of study drug exposure will be provided for each treatment arm in each treatment part in the corresponding ITT populations. Study drug compliance will be summarized in ITT_A, ITT_B_RR populations.

Study drug exposure (days) will be summarized using the sample size, mean, standard deviation, minimum, median and maximum for each treatment part. In addition

cumulative exposure of RZB will be also summarized in the ALL_RZB Population.
Study drug exposure will be summarized as follows:

Study Drug Exposure (in Days) in Each Part:

Part A:

- For subjects who did not continue into Part B:
 - Date of last injection in Part A – Date of first injection in Part A + 14 days (ADA)
 - Date of last injection in Part A – Date of first injection in Part A + 84 days (RZB)
- For subjects who continued into Part B: the minimum of
 - Date of first injection in Part B – Date of first injection in Part A.
 - Date of last injection in Part A – Date of first injection in Part A + 14 days (ADA)
 - Date of last injection in Part A – Date of first injection in Part A + 84 days (RZB)

Part B:

- Date of last injection in Part B – Date of first injection in Part B + 14 days (ADA)
- Date of last injection in Part B – Date of first injection in Part B + 84 days (RZB)

ALL_RZB:

For study drug exposure during the administration of risankizumab in the ALL_RZB Population:

- Date of last injection of risankizumab – Date of first injection of risankizumab + 84 days.

Compliance

There will be a summary of the number of subjects receiving study drug and dose at each scheduled study drug administration time point for adalimumab and for risankizumab, separately. This will be repeated on the cumulative number of doses.

When computing compliance at each scheduled time point, the denominator for each week will include all subjects in each analysis population who have not prematurely discontinued study drug (or prematurely discontinued from study) prior to the scheduled study drug injection.

Self-Administration of Risankizumab Questionnaire

There will be a summary of the self-administration of risankizumab questionnaire completed by supervising nurse/health care professional.

The following items will be summarized as-observed at each visit:

- Patient able to inject all of the liquid (Yes/No)

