Hepatic Events	Hepatic Events	Broad – Hepatic failure, fibrosis and cirrhosis and other liver damage-related conditions (SMQ 20000013) Broad – Hepatitis, non-infectious (SMQ 20000010) Broad – Cholestasis and jaundice of hepatic origin (SMQ 20000009) Broad – Liver related investigations, signs and symptoms (SMQ 20000008) Narrow – Liver-related coagulation and bleeding disturbances (SMQ 20000015)	PTs	N

Adverse Event per 100 Patient-Years of Exposure

Adverse events occurring during the entire study will be presented by event rate per 100 patient-years. These will be presented for any TEAEs, serious adverse events, Areas of Special Interest.

AEs per 100 patient-years of exposure is defined as the number of AEs divided by the total exposure in 100 patient-years. Note that one event per preferred term per day per subject will be counted in the calculation of the number of AEs (i.e., a preferred term will not be counted twice on the same day for the same subject). See the calculation method below.

$$100 \times \frac{\text{Number of TEAEs}}{\text{Total Patient Years}}$$

where total patient years is defined as the sum of the study drug exposure (defined as date of last dose – date of first dose + 105 days (5 half-lives)) of all subjects normalized by 365.25, and rounded to one decimal place.

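### The AE rates per 100 patient-years count 105 days after the last dose with no cap at the end of AE collection, so they can be understated: 0% to 1.95% for planned completers in ALL_RZB, more on other readings

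*SAP*

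**What the plan says.** SAP 11.2.1, under the rates per 100 patient-years, plans event rates over the entire study for TEAEs, serious events and Areas of Special Interest. The denominator sums, over subjects, the last-dose date minus "date of first dose + 105 days (5 half-lives)) of all subjects normalized by 365.25". The paragraph speaks of study drug. It does not say which product, whether dummy injections count, or which population is meant.

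Protocol 5.3.7 requires all AEs to be collected until the individual patient's end of trial. After that, "the investigator does not need to actively monitor the patient for AEs but should only report relevant SAEs and relevant AESIs". When the end of trial falls depends on the patient:

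- Completers who enter the extension continue on active BI 655066 there and "therefore will not have a Follow-up Visit in study 1311.30" (Protocol 6.2.3.2). Their last visit in this trial is EOT at Week 44.
- Completers who do not enter it have EOO 4 (±1) weeks after EOT, about Week 48 (Protocol 3.1).
- Patients who leave the trial early are asked back 16 (±1) "weeks after their last administered dose of BI 655066 (active or placebo") (Protocol 6.2.3.1).
- Non-extension patients who "withdraw from the study prior to their planned EOO Visit will be contacted for their vital status assessment" (Protocol 6.2.3.3). That contact records alive, dead or lost, not adverse events.

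Elsewhere the SAP does name the product. The ALL_RZB TEAE window in 11.2.1 runs to 105 days after the last risankizumab dose, and SAP 9.0 gives a formula in risankizumab injections "For study drug exposure during the administration of risankizumab in the ALL_RZB Population".

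**The concern.** A rate per unit of person-time needs events and time drawn from the same observed period. Here the denominator always receives 105 days after the last dose, while collection of non-serious events may stop sooner. Such days add patient-years and almost no events, so the error has one direction: the rate is too low.

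What is at stake is the descriptive exposure-adjusted safety profile. No primary or ranked endpoint, hypothesis test or n (%) table uses this denominator.

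Serious events are less affected, because relevant SAEs that come to the investigator's notice remain reportable after the end of trial. That protection does not cover everything in the SAP's Areas of Special Interest. The protocol's only AESI is laboratory-defined hepatic injury (5.3.6.1). SAP Table 21 also lists herpes zoster, fungal infection and hypersensitivity; when non-serious, these are neither SAEs nor the protocol's AESI, and they lose active collection at the end of trial.

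**Working it through.** **Plan's own figure.** The residual effect period in Protocol 5.3.7 and 7.3.4 is 15 weeks; 15 × 7 = 105 days, which matches the SAP. The documents state no patient-year total or rate, so there is no further figure to reproduce.

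**Inputs.** Active risankizumab: Weeks 0, 4, 16, 28 for continuers and Weeks 16, 20, 32 for switchers (Protocol Table 4.1.1: 1). BI 655066 syringes, active or placebo: last at Week 32. Active adalimumab for patients who stay on it: last at Week 41 (Table 4.1.1: 3). Patients on BI 655066 from the start also receive "1 placebo adalimumab syringe at Weeks 1, 3, 5, 7, 9, etc. up to Week 41" (Protocol 3.1). End of observation: Week 44 or Week 48.

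**Formula** (nominal days, no +1). Counted = 7 × (last dose week − first dose week) + 105. Observed = 7 × (end week − first dose week). For a given number of events the reported rate is events/counted instead of events/observed, so understatement = 1 − observed/counted, or 0 if observed is at least as long as counted.

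| Reading, completers | Dose weeks | Counted | Observed to Week 44 / 48 | Understatement |
|---|---|---|---|---|
| ALL_RZB continuers | 0–28 | 196 + 105 = 301 | 308 / 336 | 0% / 0% |
| ALL_RZB switchers | 16–32 | 112 + 105 = 217 | 196 / 224 | 9.7% / 0% |
| Any BI 655066 syringe | 0–32 | 224 + 105 = 329 | 308 / 336 | 6.4% / 0% |
| Any injection, or active adalimumab throughout | 0–41 | 287 + 105 = 392 | 308 / 336 | 21.4% / 14.3% |

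**Net effect in ALL_RZB.** Protocol 7.7 plans 300 patients per arm and assumes Week 16 adalimumab rates of 85% for PASI 50 and 45% for PASI 90. Below PASI 50: 15% of 300 = 45, all switched. Re-randomised: 40% of 300 = 120, half (60) to risankizumab. Switchers: 45 + 60 = 105.

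- Counted: 300 × 301 + 105 × 217 = 113,085 days = 309.6 patient-years.
- Unobserved if every switcher enters the extension: 105 × 21 = 2,205 days. Then 2,205/113,085 = 1.95%.
- If half enter: 0.97%. If none: 0%. The share is an assumption.
- With all entering, observed time is 110,880 days = 303.6 patient-years, so 100 events show as 32.3 instead of 32.9 per 100 patient-years.
- Other numbers of switchers, all entering: 75 give 1,575/106,575 = 1.5%; 150 give 3,150/122,850 = 2.6%.

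**Patients lost after the last dose.** Early leavers who attend EOO are seen 15 to 17 weeks (105 to 119 days) after the last BI 655066 dose, so in ALL_RZB their counted time is fully observed. Those who do not attend are not covered. If an assumed 2% of subjects had no observation after the last dose and all others entered the extension, the unobserved time is 300 × 0.02 × 105 + 105 × (0.02 × 105 + 0.98 × 21) = 3,011.4 days, or 2.7%. At 5% it is 4,221 days, or 3.7%.

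**The case against.** The strongest reply is that the effect is negligible where the SAP most plausibly means the rate to be used. ALL_RZB is the only defined safety population that spans both parts, its TEAE window and exposure formula both name risankizumab, and continuers and non-extension completers show no excess. This stands, and it is why the point is minor.

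It does not dispose of the wider reading. The rate paragraph itself says study drug and all subjects. The Week 41 figures do not depend on counting dummy injections, because patients who stay on adalimumab receive active drug to Week 41.

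The 105 days do have a rationale: they match the residual effect period and the TEAE window. That justifies the upper limit, not counting days on which AEs were no longer collected. Protocol 5.3.7 does speak of collection through the residual effect period, but it ends collection at the individual's end of trial. Protocol 3.1 places that at the last planned visit. The collection diagram is not reproduced in the text, so it could not be used as a check.

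Four stronger conclusions might be inferred and are not supported:

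- That the comparison between arms is biased. ALL_RZB has a single column, and the documents give no completion or extension shares by arm.
- That 14% to 21% is the general size. It applies only if rates cover patients staying on adalimumab or any injection counts as the last dose.
- That isolated early dropouts show a large problem. One patient can contribute much unobserved time, but the documents give no frequency for such cases.
- That SAP 9.0 already caps at the end of observation. Its rule "For subjects who continued into Part B: the minimum of" separates the study parts at the first Part B injection; the Part B and ALL_RZB formulas there have no cap.

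**Conclusion.** The point holds. The stated formula puts days without active AE collection into the denominator, and the resulting descriptive rates can only be understated.

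In ALL_RZB with risankizumab doses, the planned completers affected are the switchers who enter the extension (9.7% for that group). The net is 0% to 1.95% at the planned split. This assumes nominal dosing days, 300 continuers, 105 switchers and an extension share anywhere from 0% to 100%. The range is not a ceiling: with all entering, 75 to 150 switchers give 1.5% to 2.6%, and loss to follow-up within 105 days of the last dose adds to it.

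If the rates also cover patients who stay on adalimumab, or the last dose means any study-drug injection, completers' rates are understated by 21.4% (extension) or 14.3% (no extension). SAE rates are less affected than these figures suggest. The matter is worth correcting because it is cheap to fix and the text leaves the larger readings open; it does not threaten the trial's efficacy conclusions.

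**What to change.** For the per-100-patient-year rates only, define each subject's time at risk as the earliest of the following, minus the date of first dose:

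- last dose + 105 days;
- the last visit with active AE collection in this trial: EOT for extension entrants, EOO for others, the last attended visit for withdrawals, with contact for vital status alone not counting;
- death.

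State which populations the rates cover, and that in ALL_RZB first and last dose mean risankizumab. If other populations are shown, name the dose for each. Count the events in the rate over the same window. Leave the 105-day TEAE window for the n (%) tables as it is, and keep any SAE reported after the cap in the listings with a footnote.

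The cost is one SAP definition and minor programming from dosing, visit and death dates of this trial. Rates rise slightly in ALL_RZB. The rate numerator may differ from the TEAE table count by a few late SAEs. The rates may also no longer match the integrated safety SAP, which is not among the documents and should be checked before the change is made.

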11.2.2 SAEs (Including Deaths) and Adverse Events Leading to Study Drug Discontinuation

Deaths and all SAEs will be presented in listing format. In addition, SAEs and AE leading to study drug discontinuation will be summarized by System Organ Class and MedDRA Preferred Term.

11.2.3 Safety Subgroup Analysis

The AE overview and AE by SOC and PT in Safety_A and Safety_B_RR populations will also be analyzed with respect to the actual values of stratification factors:

- Dichotomous weight (≤ 100 kg vs. > 100 kg)
- Prior exposure to TNF antagonists (0 versus ≥ 1)

11.3 Analysis of Laboratory Data

For the assessments of laboratory data, values observed more than 105 days after the last dose of study drug will be excluded.

Listing and descriptive statistics of laboratory values over time, changes from baseline, and extreme abnormal value on treatment will be provided. Extreme abnormal value is the value which is most significantly away from the reference range. Frequency of subjects with transitions relative to reference range and listing of subjects with significant abnormal laboratory values will be presented as well.

Analyses will be conducted in the Safety_A Population, the Safety_B_RR Population, and the ALL_RZB Population.

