3.2 DISCUSSION OF TRIAL DESIGN, INCLUDING THE CHOICE OF CONTROL GROUP

This is a randomized double blind, double dummy and active controlled parallel design study. This design is appropriate for assessing the safety and efficacy of BI 655066 compared to adalimumab in patients with moderate to severe chronic plaque psoriasis. Patients will be followed up for a total of 44 weeks plus a residual effect period in order to assess the safety and maintenance of efficacy of BI 655066 compared to adalimumab.

A log of all patients enrolled into the trial (i.e. signed informed consent) will be maintained in the ISF at the investigational sites irrespective whether these patients have been treated with investigational drug or not.

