7.3.4 Safety analyses

Adverse events will be coded using the Medical Dictionary for Regulatory Activities (MedDRA) coding dictionary. Standard AbbVie summary tables and listings will be produced. All adverse events with an onset between start of treatment and end of the residual effect period (REP), a period of 15 weeks after the last administration of BI 655066 (active or placebo), will be assigned to the treatment period for evaluation.

All treated patients will be included in the safety analysis. In general, safety analyses will be descriptive in nature and will be based on AbbVie standards. No hypothesis testing is planned.

Statistical analysis and reporting of adverse events will concentrate on treatment-emergent adverse events. To this end, all adverse events occurring between start of treatment and end of the residual effect period will be considered 'treatment-emergent'. The residual effect period is defined as 15 weeks. Adverse events that start before first drug intake and deteriorate under treatment will also be considered as 'treatment-emergent'.

Frequency, severity, and causal relationship of adverse events will be tabulated by system organ class and preferred term after coding according to the current version of the Medical Dictionary for Drug Regulatory Activities (MedDRA).

Laboratory data will be analysed both quantitatively as well as qualitatively. The latter will be done via comparison of laboratory data to their reference ranges. Values outside the reference range as well as values defined as clinically relevant will be highlighted in the listings. Treatment groups will be compared descriptively with regard to distribution parameters as well as with regard to frequency and percentage of patients with abnormal values or clinically relevant abnormal values.

Vital signs, physical examinations, or other safety-relevant data observed at screening, baseline, during the course of the trial and at the end-of-trial evaluation will be assessed with regard to possible changes compared to findings before start of treatment.

More information about the safety analysis will be provided in the TSAP.

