The PP Population at Part B for re-randomized subjects (PP_B_RR) is defined as all subjects from the ITT_B_RR Population who meet all the following criteria:

- Subjects must receive at least 75% of planned risankizumab injections, as well as at least 75% of planned adalimumab injections, including dummy placebo injections, per re-randomized, in Part B.
- Subjects must have at least one PASI assessment post re-randomization in Part B.
- Subjects must have a response of PASI 50 – < 90 at re-randomization.

The primary and ranked secondary efficacy endpoint at Part B at Week 44 will be analyzed on the PP_B_RR Population.

PP Populations will be analyzed by the treatment group as randomized (or re-randomized).

Safety Populations (Safety):

The Safety Populations will be used for safety analyses in different study parts.

Each ITT Population will have a corresponding safety population (Safety) defined which require subjects to have at least one dose of active study drug during the analysis period.

Complete safety tables will be provided for the Safety_A Population and the Safety_B_RR population. AE overview tables will be provided for other safety populations.

The Safety Population will be analyzed based on the actual treatment received at the randomization visit (Safety_A) and at the re-randomization visit (Safety_B_RR).

In addition, an All Risankizumab Treated Population (ALL_RZB) is defined as all subjects who receive at least one dose of risankizumab 150 mg in the study. The ALL_RZB Population will be used for safety analyses. Complete safety tables will be provided in the ALL_RZB Population.

Notations for Treatment Groups:

Part A:

- ADA: Subjects randomized to adalimumab
- RZB: Subjects randomized to risankizumab 150 mg

Part B:

- RZB/RZB: Subjects randomized to risankizumab and continue with risankizumab
- ADA/ADA: Subjects randomized to adalimumab and stay with adalimumab at Week 16
- ADA/RZB: Subjects randomized to adalimumab and switched to risankizumab at Week 16

ALL_RZB:

- RZB: Subjects who received at least one dose of risankizumab 150 mg

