- b. The minimum of upper bound and first dose date of study drug on or after Week 16 (and within 105 days of last dose for safety analyses). If time is collected in vital signs, restrict to records prior to the first dose of study drug on or after Week 16.

Table 5. Visit Windows for Laboratory and ECG Parameters for Part A (Safety_A Population)

Window Label	Target Day	Time Window
Baseline	1	≤ 1
Week 4	29	[2, 71]
Week 16	113	[72, 155 ^a]

Rx Day calculated relative to the first dose date of study drug. For subjects randomized but not dosed, Rx Day calculated relative to randomization.

- a. The minimum of upper bound and first dose date/time on or after Week 16 (and within 105 days of last dose for safety analyses).

Table 6. Visit Windows for Other Efficacy Endpoints Only Collected at Week 16 in Part A (ITT_A Population)

Window Label	Target Day	Time Window
Baseline	1	≤ 1
Week 16	113	[2, 225 ^a]

Rx Day calculated relative to the first dose date of study drug. For subjects randomized but not dosed, Rx Day calculated relative to randomization.

- a. The minimum of upper bound and first dose date of study drug on or after Week 16.

Table 7. Visit Windows for Local Tolerability for Part A (Safety_A Population)

Window Label	Target Day	Time Window
Week 1	8	[2,15]
Week 3	22	[16, 25]
Week 4	29	[26, 71]
Week 16	113	[72, 155 ^a]

Rx Day calculated relative to the first dose of study drug. For subjects randomized but not dosed, Rx Day calculated relative to randomization.

- a. The minimum of upper bound and first dose date of study drug on or after Week 16 (and within 105 days of last dose for safety analyses) (and within 105 days of last dose for safety analyses). If time is collected in vital signs, restrict to records prior to the first dose of study drug on or after Week 16.

Table 8. Visit Windows for Analysis of PASI and sPGA in Part B (ITT_B_RR/ITT_B_R/ITT_B_NR/ITT_B_RZB/PP_B_RR Populations)

Window Label	Target Day	Time Window
Entry of B	1	≤ 1
Week 20	29	[2, 43]
Week 24	57	[44, 71]
Week 28	85	[72, 99]
Week 32	113	[100, 127]
Week 36	141	[128, 155]
Week 40	169	[156, 183]
Week 44	197	[184, 211]

Rx Day calculated relative to the first dose of study drug in Part B. For subjects re-randomized but not dosed in Part B, Rx Day calculated relative to the IRT date of re-randomization evaluation.

Table 9. Visit Windows for Laboratory and ECG Parameters for Part B (Safety_B_RR Population)

Window Label	Target Day	Time Window
Entry of B	1	≤ 1
Week 28	85	[2, 141]

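### After Week 16, no population with complete safety tables contains the adalimumab PASI 90 responders, about 135 of the 195 patients expected to stay on adalimumab

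*SAP*

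**What the plan says.** SAP 5.1 ranks the safety populations by depth of reporting: "Complete safety tables will be provided for the Safety_A Population and the Safety_B_RR population", and the same for ALL_RZB. For the rest, "AE overview tables will be provided for other safety populations". Section 11.3 then fixes the laboratory populations: "Analyses will be conducted in the Safety_A Population, the Safety_B_RR Population, and the ALL_RZB Population". Sections 11.4 (vital signs) and 11.5 (ECG) repeat that list. Section 11.6 uses Safety_A and Safety_B_RR for local tolerability, with an overall rate in ALL_RZB.

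The visit windows in SAP 6.0 agree. The Part B efficacy windows (Table 8) include the responder population ITT_B_R. The Part B windows for laboratory and ECG, vital signs and local tolerability (Tables 9, 10 and 12) are for Safety_B_RR only.

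Protocol 7.3.4 says "All treated patients will be included in the safety analysis" and "Frequency, severity, and causal relationship of adverse events will be tabulated by system organ class and preferred term". For laboratory data it adds "Treatment groups will be compared descriptively with regard to distribution parameters". Protocol 3.2 explains the 44 weeks of follow-up plus a residual effect period as being "in order to assess the safety and maintenance of efficacy of BI 655066 compared to adalimumab".

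**The concern.** Safety against adalimumab is a main objective, and the protocol ties it to the full 44 weeks. If the SAP is followed as written, the adalimumab side of any laboratory, ECG, vital-sign or all-event preferred-term statement after Week 16 comes from patients selected for partial response (PASI 50 to below 90) and re-randomised to adalimumab. The larger and better-responding part of the continuing comparator group is left out of those tables. Risankizumab, by contrast, has ALL_RZB with complete long-term tables, and no adalimumab population corresponds to it. SAP 14.1 reports that the analysis populations were defined in detail but does not mention that one group loses these tables after Week 16.

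**Working it through.** **Step 1. The plan's own figures.** Protocol 7.7 and SAP 4.3 assume 300 adalimumab patients, with Week 16 PASI 90 and PASI 50 rates of 45% and 85%. Re-randomised: 300 × (0.85 − 0.45) = 120, as stated. For 70% vs 40% at 90% power and two-sided 5%, the pooled-variance formula without continuity correction gives 56 per arm, matching Table 7.7: 1. Power at 60 per arm is 92.1%, consistent with the stated >90%.

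**Step 2. Where each group goes after Week 16.**

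| Group | Expected n | Population with complete tables after Week 16 |
|---|---|---|
| Started on risankizumab | 300 | ALL_RZB |
| Adalimumab, below PASI 50, switched | 300 × 0.15 = 45 | ALL_RZB |
| Adalimumab, re-randomised to risankizumab | 60 | Safety_B_RR and ALL_RZB |
| Adalimumab, re-randomised to adalimumab | 60 | Safety_B_RR |
| Adalimumab, PASI 90 responders | 300 × 0.45 = 135 | none |

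The responders are in Safety_A, but SAP 11.2.1 closes its event period at the first Part B dose, and the Part A windows in SAP 6.0 stop at that dose too. They are not re-randomised, so are outside Safety_B_RR. They receive no risankizumab, so are outside ALL_RZB, which is expected to hold 300 + 45 + 60 = 405 patients.

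**Step 3. Share affected.** Staying on adalimumab: 135 + 60 = 195. Without complete tables: 135/195 = 69%. Other adalimumab PASI 90 rates, with PASI 50 held at 85%:
- 50% (Table 7.7: 2): 150/(150 + 52.5) = 74%
- 55% (Table 7.7: 2): 165/(165 + 45) = 79%
- 40% (assumption): 120/(120 + 67.5) = 64%

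**Step 4. Exposure and data volume.** Weeks 16 to 44 are 196 days. Responders: 135 × 196/365.25 = 72.4 patient-years. Re-randomised to adalimumab: 60 × 196/365.25 = 32.2. So 72.4 of 104.6 patient-years fall outside the complete tables. Scheduled laboratory panels at Weeks 28 and 44: 135 × 2 = 270.

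**Step 5. What 60 rather than 195 patients can show in a summary table.** Chance of at least one case = 1 − (1 − p)^n, assuming the same risk p in every patient.
- p = 1%: 45% with n = 60, 86% with n = 195
- p = 2%: 70% with n = 60, 98% with n = 195
- No cases seen, one-sided 95% upper bound 1 − 0.05^(1/n): 4.9% with n = 60, 1.5% with n = 195

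**Step 6. A small group in no Part B population.** Under Protocol 4.1.4, a patient whose Visit 8 falls after Day 126 stays on the previous treatment whatever the PASI. An adalimumab patient in that position and below PASI 90 is neither re-randomised, nor a PASI 90 responder, nor switched, so meets none of the ITT_B_RR, ITT_B_R and ITT_B_NR definitions. The documents give no rate. If 1% to 5% of 300 are late (assumption) and 55% of these are below PASI 90, that is 300 × 0.01 × 0.55 = 1.65 to 300 × 0.05 × 0.55 = 8.25, or about 2 to 8 patients.

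**The case against.** A reader might infer that the responders have no preferred-term AE output, or no safety reporting at all, after Week 16. The documents do not support that. SAP 11.2.1 defines treatment-emergent events for Safety_B_R, and the overview covers any, related, severe and serious events, discontinuations, deaths and several areas of safety interest. Deaths and SAEs are listed. The preferred-term tables for SAEs, discontinuations and areas of safety interest (11.2.1, 11.2.2) and the rates per 100 patient-years name no population and may include the responders. For AEs the limit comes from 5.1 alone, since the table list in 11.2.1 names no population. The section 17 output list was not available and may settle this.

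A reader might also see a flat breach of Protocol 7.3.4. That is too strong. Every treated patient is in Safety_A, Protocol 7.3 bases safety analysis on treatment received at the Randomization Visit, and 7.3.4 leaves further detail to the statistical analysis plan. Nothing there promises complete tables for each Week 16 response group.

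Nor are abnormal values necessarily unseen. Clinically relevant laboratory and ECG findings are reported as AEs (Protocol 5.3.3, 5.3.4). The SAP's listings of grade 3 or higher values and of liver criteria are worded for all subjects, although they sit under 11.3 with its three populations. Step 5 therefore describes summary tables, not detection of individual cases.

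Finally, both randomised comparisons already get complete tables, and the responders have no randomised comparator, so the gap could be called a matter of reporting depth. That holds for inference. But ALL_RZB is not a randomised comparison either and still gets complete tables. The overview is also no substitute: Table 21 leaves opportunistic and fungal infections, herpes zoster, non-melanoma skin cancer, anaphylactic reaction and hepatic events out of it.

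**Conclusion.** The point holds as a stated restriction, not as one inferred from silence. For laboratory, vital-sign, ECG and local-tolerability data it follows from the populations named in 11.3 to 11.6 and from the window tables. For the preferred-term table of all treatment-emergent events it follows from 5.1.

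The 69% share is a planning expectation before dropout, and runs from 64% to 79% over PASI 90 rates of 40% to 55%. The late Visit 8 gap is real but of unknown and probably small size.

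This falls short of the 44-week purpose in Protocol 3.2 and should be corrected. It does not touch efficacy inference, the randomised Week 16 safety comparison or the monitoring of patients.

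**What to change.** - **SAP 5.1:** give complete descriptive safety tables to Safety_B_R and to a pooled group of all patients who continue adalimumab after Week 16. The pool holds the PASI 90 responders, those re-randomised to adalimumab, and anyone kept on adalimumab because Visit 8 was after Day 126. State which dose starts Part B for this last group.
- **SAP 11.3 to 11.6 and 6.0:** name both populations, and extend the windows of Tables 9, 10 and 12 to them.
- **Presentation:** no P values. Footnote that the pooled group is response-selected, because patients below PASI 50 and half of those from PASI 50 to below 90 leave adalimumab at Week 16.
- **SAP 14.1:** record the change.

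A whole-study adalimumab population mirroring ALL_RZB, ended at the first active risankizumab dose, is an optional alternative. Set beside ALL_RZB, it would invite a non-randomised comparison between response-selected groups, so the continuing-adalimumab tables are the better core change.

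The cost is one or two more sets of descriptive tables. The data are already scheduled for collection and the programs are already needed for Safety_B_RR; no visits or tests are added.
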